Assessing Feasibility, Efficacy, and Acceptability of visual feedback during HR monitoring in rehabilitation

NCT05273801

February 11, 2022

STU#: 00216223

PROTOCOL TITLE: *Assessing Feasibility, Efficacy, and Acceptability of visual feedback during HR monitoring in rehabilitation*

PRINCIPAL INVESTIGATOR:

[name] PT, DPT, PhD
 APTA Board Certified Neurologic Clinical Specialist
 Shirley Ryan AbilityLab
 [contact]
[contact]

VERSION DATE: 2.11.2022

STUDY SUMMARY:

Investigational Agent(s) (Drugs or Devices)	Heart Zones System https://heartzones.com/heart-zones-system-technical-documents/
IND / IDE / HDE #	
Indicate Special Population(s)	 Children  Children who are wards of the state  Adults Unable to Consent  Cognitively Impaired Adults  Neonates of Uncertain Viability  Pregnant Women  Prisoners (or other detained/paroled individuals)  Students/Employees
Sample Size	90
Funding Source	SRALab/PMR Department
Indicate the type of consent to be obtained	 Written  Verbal/Waiver of Documentation of Informed Consent  Waiver of HIPAA Authorization  Waiver/Alteration of Consent Process
Site	 Lead Site (For A Multiple Site Research Study)  Data Coordinating Center (DCC)
Research Related Radiation Exposure	 Yes  No
DSMB / DMC / IDMC	 Yes  No

OBJECTIVES:

The purpose of this investigation is to determine if knowledge of heart rate (HR) and target HR zones (HRzone), with visual feedback vs no feedback of HR or HRzone improves patient exercise intensity during rehabilitation. The central hypothesis for this study is with visual feedback of HR and target HR zones with instruction about exercise intensity and targets will increase patient HR intensity during sessions within a safe range set by their medical team. For purposes of this study, patients will be monitored in group and individual settings throughout the rehabilitation continuum of care sites including: inpatient rehabilitation, day rehabilitation, and

STU#: 00216223

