community fitness and will be inclusive of all individuals with chronic health conditions. Physical activity and exercise guidelines recommend everyone, including those with chronic health conditions, strive for 150 minutes of moderate intensity aerobic exercise per week.¹ This study will contribute to the knowledge of how patients achieve recommended individual HR and moderate-high intensity zones during exercise.

Aim 1: Measure the extent to which monitoring and education regarding intensity is provided (1) before HR monitoring intervention, (2) when providers know HR monitoring is occurring but without visual feedback, and (3) with visual feedback of HR monitoring.

We hypothesize providers will modify their behavior in the number of times they ask about intensity, adjust session intensity or provide education regarding intensity when visual feedback is provided compared to no feedback, which will be further increased from pre-study baseline levels.

Aim 2: Determine the efficacy of using HR with visual feedback during rehabilitation to reach target intensity.

We hypothesize participants will have higher mean HR and increased time in their individualized target HR zones when given visual feedback compared to no feedback during group sessions.

Aim 3: Determine the safety of using Heart Zones technology in rehabilitation for increasing participant exercise intensity.

We hypothesize the technology will be safe without an increase in number of adverse events throughout their rehabilitation stay.

Aim 4: Assess patient acceptability, exercise self-efficacy and confidence following use of Heart Zones technology in rehabilitation sessions.

We hypothesize use of Heart Zones technology in group settings with feedback will increase participant self-efficacy and confidence in reaching higher exercise intensities, and will be well accepted. Furthermore, we hypothesize the use of Heart Zones will be feasible in at least 75% of patient's group sessions.

Aim 5: Explore the feasibility of submax exercise testing when completed 2 times to establish individualized training targets for individuals receiving inpatient rehabilitation.

We hypothesize submax exercise testing will be feasible to perform, safe and informative to clinicians to establishing individualized heart rate zones. We believe there will be a change pre to post in submax testing indicating improvement in patient's condition.

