We will be using commercially available non-invasive, wireless HR monitors, such as the Scosche forearm monitor or other monitors with Bluetooth capability to pair with the Heart Zones platform. Scosche has a sensor with Velcro strap armband that is able to be cleaned with standard hospital cleaning procedures (Cavicide) between patient uses, yet is affordable, accessible and easy to use. Multiple heartrate monitors can be paired simultaneously and paired with a display such as an Apple IPad or other screen. Through visual display of multiple HRs in real time, it is feasible to use the Heart Zones application during a group rehabilitation session. The display monitors, HR monitors and Heart Zones platform will be stored in a locked cabinet accessible to research personnel for authorized use with this study.

PROCEDURES INVOLVED:

AIM1:

This will be conducted prior to enrollment of subjects into active phases of the study in order to understand baseline provider behavior regarding education to patients regarding intensity, monitoring of intensity and progression/modification of session intensity.

Observation of 15 sessions of each of the following conditions (total of 1500 minutes/condition):

1. Condition 1: Baseline Provider Behavior (prior to study beginning)
2. Condition 2: HR monitor on, no visual feedback
3. Condition 3: HR monitor on, visual feedback

Record number of instances in session the following occur:

- Provider provides education regarding HR/RPE/intensity
- Provider monitors HR/vitals
- Provider ask for RPE from patient
- Provider mentions target RPE/HR range
- Provider modifies task to reach target RPE/HR range

AIMS 2-5:

Screening Procedures & Consent

1. Potential subjects will be recruited from multiple settings across the continuum of rehabilitation as they are admitted.

STU#: 00216223

2. Once informed consent is obtained, screening will be performed to ensure inclusion criteria for study are met
3. Medical clearance for participation from supervising physician through online REDCap form.

2. Baseline

1. Participants will complete submax exercise test with licensed physical therapist in order to establish individualized HR intensities and zones.
 - i. Based on participant capability and timing, we will perform one or more of the submax tests or HR zone calculation methods for the individual based on clinical presentation and functional capacity.

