- Risk of loss of confidentiality will be minimized by not including personal identifying information on forms (participant will be assigned a research study number) and by conducting data collection in a private setting.

POTENTIAL BENEFITS TO PARTICIPANTS

There is likely no direct benefit to participants. Participation in this study will help researchers understanding if the use of visual feedback of HR in a group setting is feasible, efficacious and acceptable as care provided in a group model is a standard in rehabilitation.

DATA MANAGEMENT AND CONFIDENTIALITY

The analytic plan follows from the aims and the hypotheses. Descriptive statistics will be used to describe the participants and the data. Statistical tests will be utilized to assess for differences in individual outcomes baseline, mid and post through paired t-tests or appropriate non-parametric tests in consultation with a statistician. Data regarding the aims below may be analyzed for group sessions, individual sessions, and combined.

Aim 1: The null hypothesis is that there is no different in therapist behaviors to monitor/progress intensity prior to study, without visual feedback, or with visual feedback of participant's HR.

Aim 2: The null hypothesis is that there will be no difference in participant's ability to reach target intensity between sessions in which visual feedback of HR is provided and sessions where there is no visual feedback.

Aim 3: The null hypothesis is that there will be no increase in number of adverse events related to the use of Heart Zones with and without visual feedback.

Aim 4: The null hypothesis is that there will be no difference in participant exercise self-efficacy and confidence in reaching appropriate intensity when using visual feedback to no visual feedback during sessions.

Aim 5: The null hypothesis is that there will be no difference between submax exercise tests completed at baseline compared to post.

STU#: 00216223

Aim 6: The null hypothesis is that the providers will not feel the technology is appropriate, acceptable or feasible to use in a rehabilitation setting.

Data will be transferred to and stored on Shirley Ryan AbilityLab's REDCap system.

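### Aim 1 compares raw counts of provider behaviour per session without recording patients present, minutes or format, so attendance alone could move the counts

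*Combined protocol and SAP*

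**What the plan says.** Under Procedures Involved, Aim 1, the combined protocol and SAP specifies "Observation of 15 sessions of each of the following conditions (total of 1500 minutes/condition". The three conditions are baseline, monitor worn without visual feedback, and monitor worn with visual feedback. The first is "Condition 1: Baseline Provider Behavior (prior to study beginning".

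The instruction for data capture is "Record number of instances in session the following occur", followed by five provider behaviours: giving education on intensity, checking HR or vitals, asking for RPE, mentioning a target, and modifying the task to reach it. The list names no other field.

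The hypothesis under Objectives is also framed as a count: "We hypothesize providers will modify their behavior in the number of times they ask about intensity, adjust session intensity or provide education regarding intensity". The Objectives say that "patients will be monitored in group and individual settings throughout the rehabilitation continuum of care sites", which include inpatient rehabilitation, day rehabilitation and community fitness.

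The analysis text sits under Data Management and Confidentiality. For Aim 1 it gives only a null hypothesis: "The null hypothesis is that there is no different in therapist behaviors to monitor/progress intensity prior to study, without visual feedback, or with visual feedback". The general method is "Statistical tests will be utilized to assess for differences in individual outcomes baseline, mid and post through paired t-tests or appropriate non-parametric tests". On session type it says: "Data regarding the aims below may be analyzed for group sessions, individual sessions, and combined".

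**The concern.** A count of events can be compared between conditions only if the opportunity for those events is the same or is accounted for. Here opportunity has two parts: the time observed and the number of patients in the room. The plan sets a target for the first and says nothing about the second.

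Some of the five behaviours are naturally done patient by patient. A provider who asks each person for an RPE, or checks each person's HR, will log more instances in a fuller group. If the 15 sessions in one condition have more attendees, or more group sessions, than the 15 in another, the counts will differ even if every provider treats every patient identically. Aim 1 has no other comparison, so such a difference would be read as an effect of monitoring or of visual feedback. It could equally hide a real effect.

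Condition 1 is the most exposed. It precedes the study, so attendance and minutes not written down at the time may not be recoverable later.

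**Working it through.** **Inputs from Procedures Involved, Aim 1:** 15 sessions per condition; 1500 minutes per condition; 3 conditions; outcome recorded as instances per session. **Not given anywhere:** session length, group size, and the split of observed sessions between group and individual. Every value used for these below is an assumption.

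**Step 1. The plan's own figures.** Total minutes = sessions × mean length, so mean length = 1500/15 = 100 minutes. Over three conditions that is 3 × 15 = 45 sessions and 3 × 1500 = 4500 minutes. The two targets agree exactly at a mean of 100 minutes. For other assumed means:

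| Assumed mean length (min) | Minutes from 15 sessions | Sessions needed for 1500 min |
|---|---|---|
| 30 | 450 | 50 |
| 45 | 675 | 33.3 |
| 60 | 900 | 25 |
| 75 | 1125 | 20 |
| 90 | 1350 | 16.7 |
| 100 | 1500 | 15 |
| 120 | 1800 | 12.5 |

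The discrepancy can run in either direction. The plan does not say which target stops observation if the mean is not 100.

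**Step 2. What equal targets achieve.** For a behaviour paced by time, expected count = rate per minute × minutes. At 1500 minutes in each condition and an equal rate, the ratio of totals is 1500/1500 = 1.0. If both targets are met, mean length is also equal, so session length does not bias the comparison.

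**Step 3. What they do not achieve.** For a patient-directed behaviour, suppose expected count = rate per patient-minute × patient-minutes, with an equal rate in both conditions and both targets met.

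- Mean attendance of 2 v 4 (assumed): 2 × 1500 = 3000 and 4 × 1500 = 6000 patient-minutes. Ratio 6000/3000 = 2.0.
- Different format mix (assumed): individual sessions have 1 patient, groups have 4, all sessions last 100 minutes, and 6 v 9 of the 15 sessions are groups. Patient-sessions are 6×4 + 9×1 = 33 and 9×4 + 6×1 = 42. Ratio 42/33 = 1.27.
- The same mix with groups of 2: 6×2 + 9×1 = 21 and 9×2 + 6×1 = 24. Ratio 24/21 = 1.14.

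These ratios assume that counts rise in full proportion to attendance. If a provider's attention is fixed and is spread more thinly over a larger group, the ratio falls towards 1.0. The attendance effect in these examples therefore lies between none and the figure shown.

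**Step 4. Whether the analysis would remove it.** The recording list holds counts only, the Aim 1 null hypothesis has no denominator, and the general method (paired t-tests or non-parametric tests) has no exposure term. Nothing stated would adjust for the differences in Step 3.

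**The case against.** The strongest reply concerns time. The plan sets the same sessions and the same minutes in each condition, and if both are met total exposure time is balanced by design. That stands. A reader might infer from the division that 15 sessions and 1500 minutes contradict each other. The documents do not support this: they agree at 100 minutes, and no stated session length rules that out. A reader might also infer that longer sessions in one condition would inflate its counts, for example by 60/45 = 1.33 at assumed lengths of 60 v 45 minutes. That would need 900 v 675 minutes, which departs from the stated 1500 in both conditions.

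Second, a minutes target implies that someone keeps track of time, and the observation form itself is not in the documents. This is fair as far as it goes. What can be said is that the protocol's list contains no minutes per session, attendees or format, and that no stated analysis uses them.

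Third, separate analysis of group and individual sessions is allowed, which presupposes that format is known. That reduces the mixed-format problem, but the wording is optional, combined analysis is allowed too, and group size can still vary within group sessions.

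Fourth, HR recordings could supply durations. They might for monitored participants in Conditions 2 and 3. They cannot for Condition 1, which is the baseline before HR monitoring, and they would not count attendees who are not enrolled.

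Finally, not every item scales with attendance: education or a target can be given once to a whole group. That also stands, and it limits the point to patient-directed items.

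Timing should not be pressed. Only Condition 1 is labelled as preceding the study. The opening sentence of Aim 1 places the work before enrolment into the active phases, which leaves the timing of Conditions 2 and 3 unclear. The point does not depend on it.

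**Conclusion.** The point holds as a gap in recording and analysis, and no arithmetic error is shown. Aim 1 compares raw counts per session, lists no attendance, per-session minutes or format, and states no denominator, while combined group and individual analysis is allowed. The equal targets would protect against differences in total time if both are met; they give no protection against differences in attendance or format.

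The size cannot be fixed from the documents. Under the assumed group sizes and mixes above, patient-directed counts could differ by factors of up to 1.14, 1.27 or 2.0 with no change in behaviour, and by less if counts rise less than proportionally with attendance. Items delivered once to a whole group need not be affected. The consequence is limited to the interpretation of Aim 1, a process aim, and the remedy is cheap.

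**What to change.** 1. State the expected session length, and say whether sessions or minutes govern if the two diverge.
2. For each observed session, including those in Condition 1, record start and stop time, number of patients present, and group or individual format.
3. Analyse the counts as rates: a count model with log observed minutes as the offset, and log patient-minutes for the patient-directed items (RPE asked, HR or vitals checked). Adjust for format or stratify by it.
4. Where feasible, balance session format across the three conditions. This is desirable but not required, since the recorded fields allow adjustment.

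The cost is a few extra fields on the observation form, a short wording change and a slightly more complex analysis than a comparison of raw counts. The fields need to be in place before Condition 1 is observed.

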 2. Baseline measures and information will be collected from patient and medical record which include demographic information including gender, DOB, height, weight, co-morbidities, prior level of function, medical complications or concerns (pressure injuries, falls etc), precautions, admission level of function based on QI mobility items

STU#: 00216223

and outcomes measures in electronic medical record, reason for admission to rehabilitation.

3. Intervention:

1. Group and individual physical or occupational therapy sessions that are focused on endurance training (using upper and/or lower limb activities) which is a part of standard care for appropriate patients.
2. The only addition to usual standard care is the addition of a HR monitor that syncs with the Heart Zones software platform with or without visual feedback. Subjects will wear the HR monitor on their less sensory/motor impaired upper extremity.
3. There will be a continuous rolling enrollment, so some participants will receive HR feedback first while others will receive it on their second week.
4. Timing
 - i. Inpatient: 1 week of visual feedback of HR during group sessions and 1 week they will receive no feedback on their HR/zones.
 - ii. Day rehabilitation or community fitness: 2 weeks of visual feedback of HR and 2 weeks of no feedback due to fewer sessions per week.
5. Session Monitoring and Feedback
 - i. We will ask participants to rate their level of perceived exertion by using the Borg RPE Scale (6-20) at baseline, mid, and post each group session.
 - ii. Participants will answer 2 self-efficacy and confidence questions at the end of each session, rated from 0-100%.
 - iii. Subject's HR data from each session will be transferred for storage on a password protected computer accessible by approved lab staff only in order to perform summative data analysis, including peak HR, time in target HR zone, and average HR for whole session and for endurance training portion of the session.
6. We will monitor for occurrence of adverse events during sessions by assessing physiologic response to exercise, incidence of falls, etc.

4. Midpoint

1. We will collect information from their electronic medical record including new medical complications or concerns, their current functional level based on QI mobility items and outcome measures completed.

5. Post

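### Aim 1 counts providers' requests for RPE without separating out the ratings the study itself schedules in monitored group sessions, so the comparison of that item with the pre-study baseline can show a false increase

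*Combined protocol and SAP*

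**What the plan says.** The Aim 1 part of Procedures Involved sets the observation volume: "Observation of 15 sessions of each of the following conditions (total of 1500 minutes/condition"). The first condition is "Condition 1: Baseline Provider Behavior (prior to study beginning"), the second is "Condition 2: HR monitor on, no visual feedback", and the third adds the visual display. The counting instruction is "Record number of instances in session the following occur", followed by five provider behaviours, one of which is "Provider ask for RPE from patient".

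Under Objectives, the Aim 1 hypothesis is that providers ask about, adjust and teach intensity more with feedback than without, "which will be further increased from pre-study baseline levels". The null hypothesis in the Data Management and Confidentiality section spans all three conditions.

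The procedures for Aims 2-5 (item 3, Intervention, under Session Monitoring and Feedback) state: "We will ask participants to rate their level of perceived exertion by using the Borg RPE Scale (6-20) at baseline, mid, and post each group" (the sentence concerns group sessions). Here baseline means the start of the session. The schedule applies whether or not feedback is shown. The same Intervention item describes the heart-rate monitor as all that the study adds to usual care, so the RPE schedule is not treated as something that could affect Aim 1.

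**The concern.** A behaviour counted as an outcome is also a study procedure. It is scheduled in two of the three conditions and absent from the comparator. If scheduled ratings enter the count, the RPE item rises from Condition 1 to Conditions 2 and 3 in the hypothesised direction even when no provider changes practice. RPE requests are also the most direct measure of the hypothesis that providers ask about intensity more often. A reader of the results could not tell a change in provider behaviour from compliance with the study schedule. If requests are not coded when observed, the two may not be separable afterwards.

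**Working it through.** **The plan's own figure.** The only number given for Aim 1 is 15 sessions and 1500 minutes per condition, which implies 1500 / 15 = 100 minutes per session. Session length is not stated, so this cannot be confirmed. No power, effect size, variance or expected rate is given for Aim 1, so there is no sample-size calculation to reproduce.

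**Inputs from the documents.** 15 observed sessions per condition; 3 scheduled ratings per group session in Conditions 2 and 3; 0 in Condition 1.

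**Assumptions.** All 15 sessions are group sessions. Each round of ratings counts as one request. Conditions 2 and 3 are observed during intervention sessions, as the Objectives wording implies.

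**Step 1: requests added.** If the provider takes every rating and all are counted, 3 × 15 = 45 requests per condition are added. If one in three is counted on average, 1 × 15 = 15 are added. If none is counted, 0 are added.

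**Step 2: effect on the comparison with Condition 1.** Let λ be the spontaneous requests per session, the same in every condition, and c the average number of scheduled requests counted per session. The expected ratio to baseline is (λ + c) / λ. The documents give no value for λ, so a range from 0.5 to 6 was tried. False-positive rates were simulated with 15 against 15 sessions, a Welch t-test at two-sided 0.05, overdispersed spontaneous counts with variance λ + λ²/2, and 4000 runs. The Welch test is a stand-in: the plan names only paired t-tests or non-parametric alternatives, and the observed sessions are not described as paired.

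| λ (assumed) | Ratio, c = 3 | P(p<0.05), c = 3 | Ratio, c = 1 | P(p<0.05), c = 1 |
|---|---|---|---|---|
| 0.5 | 3.5/0.5 = 7.0 | 100% | 1.5/0.5 = 3.0 | 78% |
| 1 | 4/1 = 4.0 | 100% | 2/1 = 2.0 | 52% |
| 2 | 5/2 = 2.5 | 97% | 3/2 = 1.5 | 26% |
| 4 | 7/4 = 1.75 | 66% | 5/4 = 1.25 | 12% |
| 6 | 9/6 = 1.5 | 38% | 7/6 = 1.17 | 8% |

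With c = 0, the rate is about 4-5% at every λ. The problem is therefore largest where spontaneous asking is rare, and it disappears when scheduled requests are kept out of the count.

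**Step 3: effect on Condition 2 versus Condition 3.** With spontaneous rates λ₂ and λ₃, the difference is (λ₃ + c) − (λ₂ + c) = λ₃ − λ₂. The scheduled requests cancel, provided the same number per session is counted in both conditions.

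**The case against.** The strongest reply is that research staff take the scheduled ratings. The counted item names the provider, while the schedule is written in the first person plural. Elsewhere in the procedures that form means the study team, for example where it collects record data or seeks feedback from providers. On that reading a scheduled rating is not a provider request and adds nothing. This stands as a limit: the inflation is conditional. It does not settle the matter, because the protocol never says who asks and gives observers no rule.

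Three further limits also stand. The mechanical route touches one of five separately listed behaviours, and no composite is defined. The schedule covers group sessions, whereas the intervention includes individual ones and the type of the 15 observed sessions is not stated. The Aim 1 procedures also place the observations before enrolment into the active phases, yet two conditions need the monitor on. The Objectives tie those conditions to the monitoring intervention, but the timing wording should be reconciled.

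A reader might infer more than the documents support:

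- **That the item tracks the schedule whoever asks.** If staff ask, the rating could cue the provider or replace the provider's own question. Replacement would lower the count, so the direction is unknown.
- **That the feedback comparison is spoiled or diluted.** The absolute difference is not biased by this route, and the plan specifies no ratio measure.
- **That far more than 45 requests are added because several people attend each group.** The documents give neither group size nor the number of enrolled attendees.
- **That "Provider monitors HR/vitals" must fall under Condition 3 because the heart rate is on a screen.** Nothing says that reading the display does not count, and the item covers other vitals too. Comparing only manual checks with baseline would itself build in a fall.

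**Conclusion.** The concern holds in a conditional form. If treating providers take the scheduled ratings and observers count them, up to 3 requests per observed group session enter Conditions 2 and 3 and none enters Condition 1. That is 45 per condition, if all 15 sessions are group sessions and each round counts once. The comparison of this one item with the pre-study baseline can then show an increase that reflects no change in practice. With all three ratings counted, the simulated chance of a significant false difference runs from 38% to 100% over the assumed spontaneous rates of 6 down to 0.5 per session. With one in three counted, it runs from 8% to 78%. These percentages depend on the assumed rates, overdispersion and test. If research staff take the ratings there is no mechanical inflation, though cueing or substitution remains possible. The documents do not say which case applies.

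**What to change.** State in the protocol who collects the scheduled RPE. On the Aim 1 observation form, code each RPE request as protocol-scheduled or provider-initiated, and record who asked. In the analysis plan, exclude protocol-scheduled requests from the comparison with Condition 1, report the total count alongside, and rest the feedback inference for this item on Condition 2 versus Condition 3.

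The cost is a few tick-boxes and a short addition to the text, with no extra sessions or staff. The coding must be in place before sessions are observed. The downside is that scheduled ratings may replace some questions providers would otherwise have asked, so the provider-initiated count in Conditions 2 and 3 may be conservative. Reporting both counts lets the reader see the range.

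### Aim 1 hypothesises more frequent adjustment of session intensity, but the only modification item recorded counts target-directed changes, so a rise from baseline on that item could occur without more adjusting

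*Combined protocol and SAP*

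**What the plan says.** The Aim 1 hypothesis (Objectives) concerns the "number of times they ask about intensity, adjust session intensity or provide education regarding intensity". It expects more of this with visual feedback than without, "which will be further increased from pre-study baseline levels". The opening paragraph of Procedures Involved, AIM1, describes the baseline behaviour of interest as including "monitoring of intensity and progression/modification of session intensity". The Aim 1 null hypothesis (under Data Management and Confidentiality) speaks of therapist behaviours that monitor or progress intensity. None of the three makes a target a condition.

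The AIM1 recording list has five items. One concerns modification: "Provider modifies task to reach target RPE/HR range". The others cover education, monitoring of HR or vitals, asking for RPE, and "Provider mentions target RPE/HR range". No coding rule says how to score a modification when no target is in play.

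Condition 1 is placed before the study begins. The study's own targets come later: under AIMS 2-5, Baseline, consented and cleared participants have a submaximal test "in order to establish individualized HR intensities and zones", or have zones set by one of the listed alternatives.

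**The concern.** The outcome is hypothesised in one form and recorded in a narrower one, and the narrowing may not act equally across conditions. Before the study, a provider may speed up, slow down or load a task by judgement alone, and the form has no row for that. Once participants have individual zones, the same number of adjustments may more often be made with a target in view and so be counted.

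The hypothesis predicts a rise from baseline, so any bias of this kind runs in the hypothesised direction. At stake is the reading of one item in the comparisons of Conditions 2 and 3 with Condition 1: a rise could mean that providers adjust more often, or that they adjust as often as before with a target more often in view. The form as written cannot separate the two.

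**Working it through.** **No plan figure to reproduce.** The documents give no significance level, power, effect size or event rate for Aim 1. The check is a comparison of definitions, followed by an illustration.

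**Definitions side by side**

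| Place | Behaviour | Target required? |
|---|---|---|
| Objectives, Aim 1 hypothesis | adjusting session intensity | no |
| Procedures, AIM1, opening paragraph | progressing or modifying intensity | no |
| Data Management, Aim 1 null | monitoring or progressing intensity | no |
| Procedures, AIM1, recorded item | modifying a task towards a target range | yes |

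**Availability of targets.** Study-issued zones do not exist in Condition 1. I take them to exist in Conditions 2 and 3, which need participants wearing the monitor. Usual-care targets may exist in any condition. The Background says HR zones and RPE are often used in rehabilitation without a submaximal test, and that the extent to which intensity recommendations are applied is unknown, particularly in group therapy.

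**Illustration.** From the plan: 15 sessions per condition. Assumed: *r* adjustments per session, equal in both conditions, and a codable share *s* (the fraction made to reach a target).

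- Expected recorded count: m = 15 × r × s.
- Apparent ratio against Condition 1: m₁/m₀ = s₁/s₀. It does not depend on r or on the number of sessions.
- Approximate chance of a significant rise (Poisson counts, two-sided 5%): Φ(√2 × (√m₁ − √m₀) − 1.96).

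Worked case, r = 4, shares 50% and 75%: m₀ = 15 × 4 × 0.50 = 30 and m₁ = 15 × 4 × 0.75 = 45. The ratio is 1.5. √45 − √30 = 6.708 − 5.477 = 1.231; 1.414 × 1.231 − 1.96 = −0.22; Φ(−0.22) ≈ 0.41.

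| Share, Condition 1 to later condition | Apparent ratio | r = 2 | r = 4 | r = 8 |
|---|---|---|---|---|
| 50% to 50% | 1.0 | 2.5% | 2.5% | 2.5% |
| 50% to 75% | 1.5 | 23% | 41% | 69% |
| 25% to 50% | 2.0 | 36% | 62% | 89% |
| 25% to 75% | 3.0 | 81% | 98% | about 100% |

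**Sensitivity to the test.** Simulating a conditional binomial test on Poisson counts gives somewhat lower two-sided rejection rates. For r = 4 they are 97% (25% to 75%) and 37% (50% to 75%); for r = 2, about 75% and 18%. The plan names paired t-tests or non-parametric tests. A Mann-Whitney test on session counts with strong assumed between-session variation (gamma, shape 1) lowers the four to about 50%, a little over 10%, 40% and 10%.

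**With every modification counted,** the share is 100% in each condition, the ratio is 1.0 when the true rate is unchanged, and the chance of a false rise returns to the nominal 2.5%.

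**The case against.** Four arguments on the other side have weight.

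- **A zone on file does not score an event.** The item asks for a modification made to reach a target, in every condition. A provider who never works to a target scores zero throughout. For the count to rise, providers must start working to targets, which is itself a change in behaviour. This stands, but it is a change in the purpose of adjustments, whereas the hypothesis concerns how often they are made.
- **Usual care already has targets.** The item covers RPE as well as HR, and the Background describes RPE scales and HR formulas as established tools. This also stands. A reader might infer that Condition 1 counts are forced to zero, or that a false positive is built in; the documents support neither. Equally, they give no ground for assuming equal shares before and after zones are issued.
- **Targets are part of what is studied.** The Objectives speak of knowledge of target zones and instruction about them, so more target-directed modification can be an intended effect. That is a reason to keep the target-linked count. It does not make that count a measure of adjustment frequency.
- **The hypothesis is a summary and the list is the operational definition.** Neither the hypothesis nor the opening paragraph says that any adjustment counts. But nothing in the text signals that the narrower item was a deliberate restriction.

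A reader might also extend the point to "Provider mentions target RPE/HR range". That does not follow: mentioning a target is openly a target behaviour, more mentions are a real change, and Aim 1 can properly compare them with baseline.

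**Conclusion.** The mismatch is real and confined to one of the five recorded items. Because the codable share of adjustments may be lower before the study issues zones, a rise from Condition 1 on that item is possible with no change in how often providers adjust intensity. The size of the bias is unknown. The ratios of 1.5 to 3.0 and the rejection rates above rest on assumed shares, assumed adjustment rates and, for the higher rates, counts with no extra variation between sessions. The 97% to 98% figures belong to one of the less cautious combinations and should not be read as an estimate for this trial.

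Condition 3 versus Condition 2 is largely unaffected, provided study zones exist in both. The other four items need no change on this account.

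**What to change.** On the Aim 1 observation form, replace the modification row with one that records every provider modification of task intensity, up or down, in all three conditions. Add a tick-box for modifications made to reach a stated RPE or HR target range.

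In the Aim 1 analysis, use all modifications as the adjustment outcome across Conditions 1 to 3. Report target-linked modifications as a secondary count, noting that study-issued zones exist only in Conditions 2 and 3. Leave the item on mentioning a target, and its baseline comparison, as planned.

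The cost is one reworded row, one tick-box, a sentence in the analysis section and slightly more coding work for the observer. No information is lost, since the present item can be recovered from the tick-box. The change has to precede the Condition 1 observations. If those have already been made on the present form, the uncounted adjustments cannot be recovered from it, and the baseline comparison should be described as target-directed modification only.
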